##### **4.2.8.1 Definition**

- Population: Full analysis set
- Endpoint: Number of hospital admissions or ED visits with HK as a contributing factor at any time post-discharge up to 180 days.
- Intercurrent event strategy: Participants who discontinue treatment, use rescue therapy for HK or who have a hospital admission or an ED visit without HK as a contributing factor, will continue to be followed up to the first component of the composite endpoint (treatment policy strategy). Participants who die of any cause or are lost to follow-up will be censored at the date of death or loss to follow-up. Participants who have RAASI down-titration (including discontinuation) will continue to be followed up to the first component of the composite endpoint (treatment policy strategy).
- Population level summary (analysis): Mean number of hospital admissions or ED visits, with HK as a contributing factor by randomised treatment group. Negative binomial regression model with randomised treatment group as the independent variable and including duration of time in study as an offset. The incidence rate (SZC/SoC), along with 95% confidence intervals and two-sided p-values will be displayed.

##### **4.2.8.2 Derivations**

For each participant the total number of separate hospital admissions or ED visits with HK as a contributing factor up to 180 days will be calculated. Hospital admissions and ED visits will be calculated as separate admissions if start and stop dates of admission do not overlap. If hospital admissions or ED visits are missing a start, stop date or both then they

will be calculated as separate admissions. Hospital admissions or ED visits started after 180 days will not be counted.

#### **4.2.8.3 Handling of Dropouts and Missing Data**

All available data on hospital admissions and ED visits are to be used irrespective of intercurrent events. For the primary analysis, no adjustment is made for dropout but the sensitivity of the results to this approach are investigated using a sensitivity analysis in section 4.2.5.5.

#### **4.2.8.4 Primary Analysis of Secondary Endpoint #6**

The primary analysis of this secondary endpoint will be performed as per section 4.2.5.4.

#### **4.2.8.5 Sensitivity Analyses of the Secondary Endpoint #6**

Sensitivity analyses of this secondary endpoint will be performed as per section 4.2.5.5.

#### **4.2.8.6 Supplementary Analyses of the Secondary Endpoint #6**

Not Applicable.

#### **4.2.8.7 Subgroup Analyses**

Subgroup analyses will be performed using separate negative binomial regression models, as per section 4.2.5.4, by presence of heart failure (Yes/No, identified per Medical History using an SMQ of “Cardiac Failure”; SMQ Code: 20000004), RAASI use at screening (Yes/No, identified per Concomitant Medication eCRF as CMCLASCD in (‘C09AA’, ‘C09BA’, ‘C09BB’, ‘C09BX’, ‘C09CA’, ‘C09DA’, ‘C09DB’, ‘C09DX’, ‘C09XA’) where Start Date is prior to date of informed consent), CKD stage, without diagnosis of CKD (but eGFR <90 ml/min/1.73m^2), baseline K+ (5.0 < K+ ≤ 5.5 versus 5.5 < K+ ≤ 6.5 mmol/L) at baseline and an alternative baseline K+ categorisation (5.0 < K+ ≤ 5.5, 5.5 < K+ ≤ 6.0, and 6.0 < K+ ≤ 6.5 mmol/L) at baseline. Subgroup analyses will only be conducted providing there are 10 or more events per subgroup category.

### **4.2.9 Exploratory Endpoint #1 (Hospital admission/ED visit with HK, all-cause death)**

*Time to first occurrence of any component of hospital admission or ED visit, both with HK as a contributing factor, or all-cause death at any time post-discharge up to 180 days inclusive.*

#### **4.2.9.1 Definition**

- Population: Full analysis set
- Endpoint: Time to first occurrence of either component of the composite outcome at any time post-discharge up to 180 days inclusive.
- Intercurrent event strategy: Participants who discontinue of treatment will continue to be followed up to the first component of the composite endpoint (treatment policy

strategy). Participants who require hospital admission or ED visits without HK as a contributing factor or use rescue therapy will continue to be followed up to the first component of the composite endpoint (treatment policy strategy). Participants who die of any cause will be considered an event (composite variable strategy). Participants who are lost to follow-up will be censored at the date of loss to follow-up. Participants who have RAASi down-titration (including discontinuation) will continue to be followed up to the first component of the composite endpoint. Participants who do not have an event by 180 days post-discharge will be administratively censored at the date of 180 days post-discharge.

- Population level summary (analysis): Kaplan-Meier plots of the survival function for the SZC and SoC treatment groups will be presented. Log-rank test for testing will be used to calculate a two-sided p-value, Cox proportional hazards ratio for estimation, with randomised treatment group (reference level SoC) as the independent variable. The HR and the two-sided 95% confidence interval will be presented. The risk difference and two-sided 95% confidence interval will be presented (as per section 4.2.3.2) at 180 days post-discharge.

#### **4.2.9.2 Derivations**

Time to first occurrence will be defined as the earliest date of (hospital admission or ED visits with HK as a contributing factor, all-cause death, date of loss to follow-up, date of 180 days post-discharge) – date of randomization + 1.

#### **4.2.9.3 Handling of Dropouts and Missing Data**

Participants who are lost to follow-up will be censored at the date of discontinuation as recorded on the participant's disposition form.

#### **4.2.9.4 Primary Analysis of Exploratory Endpoint #1**

The primary analysis of this exploratory endpoint will be performed as per section 4.2.3.4.

#### **4.2.9.5 Sensitivity Analyses of Exploratory Endpoint #1**

Sensitivity analyses of this exploratory endpoint will be performed as per section 4.2.3.5.

#### **4.2.9.6 Supplementary Analyses of Exploratory Endpoint #1**

Not Applicable.

#### **4.2.9.7 Subgroup Analyses**

Not Applicable.

### **4.2.10 Exploratory Endpoint #2 (Hospital admission with HK, all-cause death)**

*Time to first occurrence of either hospital admission with HK as a contributing factor or all-cause death at any time post-discharge up to 180 days inclusive.*

#### **4.2.10.1 Definition**

- Population: Full analysis set
- Endpoint: Time to first occurrence of either component of the composite outcome at any time post-discharge up to 180 days inclusive.
- Intercurrent event strategy: Participants who discontinue of treatment will continue to be followed up to the first component of the composite endpoint (treatment policy strategy). Participants who require hospital admission without HK as a contributing factor or any ED visits or who use rescue therapy will continue to be followed up to the first component of the composite endpoint (treatment policy strategy). Participants who die of any cause will be considered an event (composite variable strategy). Participants who are lost to follow-up will be censored at the date of loss to follow-up. Participants who have RAASi down-titration (including discontinuation) will continue to be followed up to the first component of the composite endpoint (treatment policy strategy). Participants who do not have an event by 180 days post-discharge will be administratively censored at the date of 180 days post-discharge.
- Population level summary (analysis): Kaplan-Meier plots of the survival function for the SZC and SoC treatment groups will be presented. Log-rank test for testing will be used to calculate a two-sided p-value, Cox proportional hazards ratio for estimation, with randomised treatment group (reference level SoC) as the independent variable. The HR and the two-sided 95% confidence interval will be presented. The risk difference and two-sided 95% confidence interval will be presented (as per section 4.2.3.2) at 180 days post-discharge.
- Sensitivity analyses will be conducted as per secondary endpoint #1.

#### **4.2.10.2 Derivations**

Time to first occurrence will be defined as the earliest date of (hospital admission with HK as a contributing factor, all-cause death, date of loss to follow-up, date of 180 days post-discharge) – date of randomization + 1.

#### **4.2.10.3 Handling of Dropouts and Missing Data**

Participants who are lost to follow-up will be censored at the date of discontinuation as recorded on the participant's disposition form.

#### **4.2.10.4 Primary Analysis of Exploratory Endpoint #2**

The primary analysis of this other endpoint will be performed as per section 4.2.3.4.

#### **4.2.10.5 Sensitivity Analyses of Exploratory Endpoint #2**

Sensitivity analyses of this exploratory endpoint will be performed as per section 4.2.3.5.

#### **4.2.10.6 Supplementary Analyses of Exploratory Endpoint #2**

Not Applicable.

#### **4.2.10.7 Subgroup Analyses**

Not Applicable.

#### **4.2.11 Exploratory Endpoint #3 (ED visit with HK, all-cause death)**

*Time to first occurrence of either ED visit with HK as a contributing factor or all-cause death at any time post-discharge up to 180 days inclusive.*

##### **4.2.11.1 Definition**

- Population: Full analysis set
- Endpoint: Time to first occurrence of either component of the composite outcome at any time post-discharge up to 180 days inclusive.
- Intercurrent event strategy: Participants who discontinue of treatment will continue to be followed up to the first component of the composite endpoint (treatment policy strategy). Participants who require any hospital admission or ED visits without HK as a contributing factor or who use rescue therapy will continue to be followed up to the first component of the composite endpoint (treatment policy strategy). Participants who die of any cause will be considered an event (composite variable strategy). Participants who are lost to follow-up will be censored at the date of loss to follow-up. Participants who have RAASi down-titration (including discontinuation) will continue to be followed up to the first component of the composite endpoint (treatment policy strategy). Participants who do not have an event by 180 days post-discharge will be administratively censored at the date of 180 days post-discharge.
- Population level summary (analysis): Kaplan-Meier plots of the survival function for the SZC and SoC treatment groups will be presented. Log-rank test for testing will be used to calculate a two-sided p-value, Cox proportional hazards ratio for estimation, with randomised treatment group (reference level SoC) as the independent variable. The HR and the two-sided 95% confidence interval will be presented. The risk difference and two-sided 95% confidence interval will be presented (as per section 4.2.3.2) at 180 days post-discharge.

##### **4.2.11.2 Derivations**

Time to first occurrence will be defined as the earliest date of (ED visit with HK, all-cause death, date of loss to follow-up, date of 180 days post-discharge) – date of randomization + 1.

##### **4.2.11.3 Handling of Dropouts and Missing Data**

Participants who are lost to follow-up will be censored at the date of discontinuation as recorded on the participant's disposition form.

##### **4.2.11.4 Primary Analysis of Exploratory Endpoint #3**

The primary analysis of this other endpoint will be performed as per section 4.2.3.4.

#### **4.2.11.5 Sensitivity Analyses of the Exploratory Endpoint #3**

Sensitivity analyses of this exploratory endpoint will be performed as per section 4.2.3.5.

#### **4.2.11.6 Supplementary Analyses of the Exploratory Endpoint #3**

Not Applicable.

#### **4.2.11.7 Subgroup Analyses**

Not Applicable.

### **4.2.12 Exploratory Endpoint #4 (All-cause hospitalisations, ED visits, use of rescue therapy for HK, all-cause death)**

*Time to first occurrence of any component of all-cause hospitalisations, ED visits, use of rescue therapy for HK or all-cause death in each arm at any time post-discharge up to 180 days.*

#### **4.2.12.1 Definition**

- Population: Full analysis set
- Endpoint: Time to first occurrence of any component of all-cause hospitalisations, ED visits, use of rescue therapy for HK or all-cause death in each arm at any time post-discharge up to 180 days.
- Intercurrent event strategy: Participants who discontinue of treatment will continue to be followed up to the first component of the composite endpoint (treatment policy strategy). Rescue therapy for HK will be considered an event (composite variable strategy). Participants who require any hospital admission or ED visit will be considered an event (composite variable strategy). Participants who die of any cause will be considered an event (composite variable strategy). Participants who are lost to follow-up will be censored at the date of loss to follow-up. Participants who have RAASI down-titration (including discontinuation) will continue to be followed up to the first component of the composite endpoint (treatment policy strategy). Participants who do not have an event by 180 days post-discharge will be administratively censored at the date of 180 days post-discharge.
- Population level summary (analysis): Kaplan-Meier plots of the survival function for the SZC and SoC treatment groups will be presented. Log-rank test for testing will be used to calculate a two-sided p-value, Cox proportional hazards ratio for estimation, with randomised treatment group (reference level SoC) as the independent variable. The HR and the two-sided 95% confidence interval will be presented. The risk difference and two-sided 95% confidence interval will be presented (as per section 4.2.3.2) at 180 days post-discharge.

#### **4.2.12.2 Derivations**

Time to first occurrence will be defined as the earliest date of (all-cause hospital admission, all-cause ED visit, all-cause death, use of rescue therapy for HK, date of loss to follow-up, date of 180 days post-discharge) – date of randomization + 1.

#### **4.2.12.3 Handling of Dropouts and Missing Data**

Participants who are lost to follow-up will be censored at the date of discontinuation as recorded on the participant's disposition form.

#### **4.2.12.4 Primary Analysis of Exploratory Endpoint #3**

The primary analysis of this exploratory endpoint will be performed as per section 4.2.3.4.

#### **4.2.12.5 Sensitivity Analyses of the Exploratory Endpoint #3**

Sensitivity analyses of this exploratory endpoint will be performed as per section 4.2.3.5.

#### **4.2.12.6 Supplementary Analyses of the Exploratory Endpoint #3**

Not Applicable.

#### **4.2.12.7 Subgroup Analyses**

Not Applicable.

### **4.2.13 Exploratory Endpoint #5 (K+ up to 180 days post-discharge)**

*Potassium level up to 180 days post-discharge.*

#### **4.2.13.1 Definition**

- Population: Full analysis set
- Endpoint: Potassium levels up to 180 days post-discharge.
- Intercurrent event strategy: Potassium levels from participants after discontinuation of treatment, hospital admissions, or ED visits for any reason will be included in the analysis (treatment policy strategy). Participants who use rescue therapy for HK will have K+ levels prior to rescue therapy for HK used in the analysis (while on treatment strategy). Participants who have RAASI down-titration (including discontinuation) will have K+ levels prior to the RAASI down-titration used in the analysis (while on treatment strategy). Participants who die of any cause or who are lost to follow-up prior to 180 days post-discharge will have all available K+ included in the analysis (treatment policy strategy).
- Population level summary (analysis): A mixed model repeated measures (MMRM) analysis, described in section 4.2.13.4, will be used. The population level summary will be the coefficient estimates, standard error, 95% CI for coefficient estimate, and p-values for the randomised treatment group term.

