
To evaluate the effect of continuing SZC as part of the discharge medications, compared to SoC, on mean K⁺ levels	
Population: Full analysis setEndpoint: K⁺ level up to 180 days post-discharge.Intercurrent event strategy: K⁺ levels from participants after discontinuation of treatment, hospital admissions or ED visits for any reason will be included in the analysis (treatment policy strategy). Participants who use rescue therapy for HK will have K⁺ levels prior to rescue therapy for HK used in the analysis (while on treatment strategy). Participants who have RAASI down-titration (including discontinuation) will have K⁺ levels prior to the RAASI down-titration used in the analysis (while on treatment strategy). Participants who die of any cause or who are lost to follow-up prior to 180 days post-discharge will have all available K⁺ included in the analysis (treatment policy strategy).Population level summary (analysis): Mixed model repeated measures analysis with randomised treatment group as an independent variable. The coefficient estimates, standard error, 95% confidence intervals for coefficient estimate, and p-values will be reported.

To evaluate the effect of continuing SZC as part of the discharge medications, compared to SoC, in reducing the number of hospital admissions with HK as a contributing factor	
Population: Full analysis setEndpoint: Number of hospital admissions with HK as a contributing factor, at any time post-discharge up to 180 days.Intercurrent event strategy: Participants who discontinue treatment, use rescue therapy for HK, have RAASI down-titration (including discontinuation), experience all-cause death or loss to follow-up prior to 180 days post-discharge will have all available hospital admission data used irrespective of the intercurrent event (treatment policy strategy).Population level summary: Mean number of hospital admissions with HK as a contributing factor, by randomised treatment group. Negative binomial regression model with randomised treatment group as a main effect and including duration of time in study as an offset. The incidence rate ratio (SZC/SoC), along with 95% confidence intervals and two-sided p-values will be displayed.

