4.2 Scientific Rationale for Study Design

Hospitalised CKD patients with HK are at higher risk of recurrent HK and of readmission than hospitalised CKD patients without HK.

CONTINUITY will recruit hospitalised participants with CKD (see inclusion criterion [#3](#) for details) and HK (see inclusion criterion [#4](#) for details). After treatment with SZC, the participants reaching NK will be randomised to either SZC or SoC treatment at discharge. The study aims to show that prescribing SZC as a part of the discharge medications in this population will result in an increased likelihood of maintained NK and a reduced incidence of all-cause hospital admissions or ED visits with HK as a contributing factor, compared with participants discharged with SoC.

The study interventions are SZC (as per local label) and SoC (as per local practice) groups. Participants in both groups will have K⁺ normalised at the beginning of the outpatient phase and monitoring of K⁺ will occur during study. Titration of SZC will be based on K⁺ values, according to Section 6.2 to ensure participants receive SZC at an individually optimised dose. Clear guidance is in place for rescue therapy for HK (see Section 6.7.1) as well as for study discontinuation (see Section 7).

The SoC as per local practice is used as comparator as there is currently no standardised therapy to treat patients with CKD and HK after discharge from the hospital.

The study is designed to align as much as possible with real-world clinical practice, with low number of mandated on-site follow-up visits (at Days 7, 90, and 180 post-discharge) and by using medical chart reviews and telephone contacts in between for complementary data collection.

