#### **4.2.13.2 Derivations**

Time from randomisation will be calculated as date of  $K^+$  - date of randomisation + 1.

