#### **4.2.13.4 Primary Analysis of Exploratory Endpoint #5**

A MMRM will be fitted in the FAS with  $K^+$  measurements as the dependent variable and randomised treatment group (reference level SoC), time from randomisation, country and the interaction of treatment group by time from randomisation with random effects for participant, intercept and slope. The covariance structure will be unstructured. The coefficient estimates, standard error, 95% CI for coefficient estimates, and p-values will be reported. The model assumptions will be assessed by plotting a histogram of the model residuals and a scatter plot of the model residuals versus predicted values.

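### The named summary of the exploratory K+ model is the arm difference at about randomisation, not the effect on mean K+ up to 180 days

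*SAP*

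**What the plan says.** The objective is the effect of continuing SZC on mean K+ levels, and the endpoint is K+ up to 180 days post-discharge (Protocol section 3; SAP 4.2.1 and 4.2.13.1).

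- **Model (SAP 4.2.13.4).** K+ is regressed on treatment, with SoC as reference, plus "time from randomisation, country and the interaction of treatment group by time from randomisation with random effects for participant, intercept and slope". A random slope on time means that time is continuous.
- **Time scale (SAP 4.2.13.2).** Time is the K+ date minus "date of randomisation + 1". The day of randomisation is therefore t = 1. No centring is stated.
- **Summary (SAP 4.2.13.1).** The population-level summary is the coefficient estimate, standard error, 95% CI and p-"values for the randomised treatment group term".
- **Output (SAP 4.2.13.4).** "The coefficient estimates, standard error, 95% CI for coefficient estimates, and p-values will be reported", with no restriction to one term. The overview in SAP 4.2.1 reads the same way.
- **Protocol section 3.** "Mixed model repeated measures analysis with randomised treatment group as an independent variable"; no interaction is listed there or in Protocol 9.4.3.3.
- **State at randomisation (Protocol 4.2).** "Participants in both groups will have K⁺ normalised at the beginning of the outpatient phase".

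No arm difference at a stated day, and no average over follow-up, is specified for this endpoint.

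**The concern.** Once a model contains treatment-by-time, the treatment coefficient is no longer an overall arm difference. It is the difference where the time variable equals zero, which here is about randomisation. At that point every participant has just been on SZC and must be normokalaemic to be randomised, so the true difference is expected to be near zero. The quantity of interest lies later in follow-up and needs the treatment and interaction terms together.

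Two features suggest an oversight. For the eGFR model of similar form, SAP 4.2.22.4 says that the interaction carries the evidence; the K+ section has no such sentence. And the protocol's model lists treatment without an interaction, so there the treatment coefficient would be an overall difference. The SAP added the interaction but kept treatment as the summary, and SAP section 2 does not list the change.

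At stake is a pre-specified estimate and p-value that may not describe the effect on mean K+, and whose meaning shifts with choices that the SAP leaves open.

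**Working it through.** The documents give no power, sample size or expected effect for this endpoint, so there is no planned figure to reproduce.

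**Step 1: what the named term estimates.** Leaving country aside, E[K+] = b0 + b1·trt + b2·t + b3·trt·t. The arm difference at time t is b1 + b3·t. The named summary is b1, the difference at t = 0. Under the SAP's +1 convention that is the day before randomisation, which differs immaterially from randomisation itself.

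**Step 2: which records may enter.** Protocol 8.1.1 uses central-laboratory values for endpoints. Central samples are taken at discharge, Day 90, Day 180 and early discontinuation; Day 7 is local only. SAP 4.2.13.3 uses all available K+ up to rescue therapy and excludes neither discharge nor local values. By contrast, SAP 4.2.22.1 specifies post-randomisation values as the outcome for eGFR, with the value at randomisation as a covariate. Several record sets are therefore compatible with the K+ text.

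**Step 3: project assumed trajectories onto the model.** With complete records at common visit days, and random intercept and slope on the same time variable, the fitted b1 and b3 are on average the least-squares line through the true arm differences. No SD or effect size is needed, only a trajectory and visit days. Set the true Day 180 effect to 1 and t = visit day + 1.

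*Linear growth from zero at randomisation:* d(t) = (t − 1)/180, so b1 = −1/180 = −0.006, in effect 0%.

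*Constant effect; discharge, Day 90, Day 180:* t = 1, 91, 181 and d = 0, 1, 1. Slope = 90/(8100 + 0 + 8100) = 0.00556. b1 = 0.667 − 0.00556 × 91 = 0.16.

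*Constant effect; discharge, Day 7, Day 90, Day 180:* t = 1, 8, 91, 181 and d = 0, 1, 1, 1. Mean t = 70.25; slope = 69.25/21366.75 = 0.00324. b1 = 0.75 − 0.00324 × 70.25 = 0.52.

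*Constant effect; post-randomisation records only:* d = 1 throughout, so b1 = 1.00 and b3 = 0.

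*Half the effect at Day 7, full from Day 90; Days 7, 90, 180:* t = 8, 91, 181 and d = 0.5, 1, 1. Slope = 42.67/14972.67 = 0.00285. b1 = 0.833 − 0.00285 × 93.33 = 0.57.

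*Effect narrowing linearly from Day 7 to half its size at Day 180; Days 7, 90, 180:* slope = −0.5/173 = −0.00289 per unit of the Day 7 effect. b1 = 1 + 8 × 0.00289 = 1.02 of the Day 7 effect, which is 1.02/0.5 = about 2 times the Day 180 effect.

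| Assumed trajectory | Records | b1 as share of Day 180 effect | b1 + b3·181 as share |
|---|---|---|---|
| Grows linearly from 0 | any of these sets | about 0% | 100% |
| Constant | discharge/90/180 | 16% | 117% |
| Constant | discharge/7/90/180 | 52% | 111% |
| Half at Day 7, full from Day 90 | 7/90/180 | 57% | 108% |
| Constant | post-randomisation only | 100% | 100% |
| Narrows to half by Day 180 | 7/90/180 | about 205% | 100% |

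The last column exceeds 100% where a straight line is fitted to a curved difference. The Day 180 contrast still stays within 17% of the truth, while b1 ranges from about 0% to about 205%.

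**Step 4: illustration by simulation.** Assumptions, none taken from the documents except N: N = 130, effect −0.4 mmol/L, between-participant SD 0.35, slope SD 0.2 per 180 days, residual SD 0.4, 40 replicates per case. Under linear growth the mean treatment term lay between −0.01 and +0.02 with p < 0.05 in 2–10% of runs; the interaction was significant in 92–100%. Under a constant effect the treatment term averaged −0.43 with Days 7/90/180 (p < 0.05 in 100%), −0.07 with discharge/90/180 (10%) and −0.20 with discharge/7/90/180 (72%). With few replicates and convergence warnings in some fits, these figures only illustrate; the conclusion rests on Steps 1 and 3.

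**The case against.** **The interaction will probably be shown.** SAP 4.2.13.1 defers to 4.2.13.4 for the analysis, and that section and the overview report coefficient estimates generally. This stands. A reader might infer from 4.2.13.1 that only the treatment term is reported, but the documents do not say so. The fault lies in which term is declared the summary. Printing both coefficients does not fully repair it: the point estimate b1 + b3·t can be formed by hand, but its interval also needs the covariance of the two estimates, which is not in the listed output.

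**The effect need not grow slowly from zero.** Protocol 4.3 describes K+ reduction within 1 hour of a dose and normokalaemia in most participants within 24 to 48 hours. Arm B leaves hospital without SZC, so the arms may separate within days. From Day 7 Arm B may be given a K-binder, which could narrow later differences. With post-randomisation records only, an early and sustained effect is recovered in full, and a narrowing one is exceeded. This also stands. A reader might infer that a real K+ effect will be reported as zero; that follows only if the difference grows linearly from zero, and the documents do not establish that trajectory.

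**Little depends on it.** The endpoint is exploratory and absent from the testing order in SAP Table 5. This is correct and sets the severity.

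None of these points makes b1 an estimate of the effect on mean K+ up to 180 days. It coincides with that effect only under particular combinations of trajectory and records.

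**Conclusion.** The point holds as a minor specification error. The summary named in SAP 4.2.13.1 does not match the model in 4.2.13.4: it is the arm difference extrapolated to about randomisation. That follows from the model's form and needs no numerical assumption.

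The size of the mismatch does rest on assumptions about trajectory and visit days. Across the cases examined the term ranges from about 0% to about twice the Day 180 effect. The 16% case corresponds to a constant effect on the central-laboratory schedule that the protocol assigns to endpoint assessment, if discharge K+ is treated as an outcome. Neither a null result nor a faithful one can be predicted from the documents. No confirmatory claim, sample size or primary result is affected.

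**What to change.** In SAP 4.2.13.1, make the population-level summary the model-based SZC minus SoC difference in mean K+ at Day 180, with 95% CI and p-value. Add the difference at Day 90 or the average over follow-up. Report the treatment-by-time term alongside. If a straight-line difference is doubted, treating visit as categorical with least-squares mean differences serves the same purpose.

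In SAP 4.2.13.3 or 4.2.13.4, state whether discharge K+ is an outcome record, a covariate or neither, and whether local Day 7 values enter. The adjusted model in 4.2.13.5 lists no time or interaction term; it should carry the same ones so that its result is comparable.

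The cost is a few sentences of SAP text and one estimate statement in the program. No new data are needed.
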